- **7.3.2 Monitoring**. The risks of haloperidol and ziprasidone include tardive dyskinesia, neuroleptic malignant syndrome (NMS), extrapyramidal side effects (EPS), torsades de pointes and other arrhythmias, and hyperglycemia. Throughout the Treatment Period, study personnel will carefully monitor all patients daily for evidence of these potential adverse effects, determine study drug efficacy and safety, and monitor other factors that may influence outcomes. The above section describes how study drug will be titrated, held, or permanently discontinued should adverse effects occur. Additionally, all patients will be monitored carefully throughout the Post-Study Drug Period, which includes the four full calendar days after study drug is discontinued. Note: For patients who receive no study drug after day 10 post-randomization, daily monitoring will conclude at the end of the Treatment Period (i.e., at hospital discharge, death, or day 14 post-randomization, whichever occurs first) because the Post-Study Drug Period for these patients will be contained within the Treatment Period. Alternatively, patients who continue to receive study drug after day 10 post-randomization will be monitored through the end of the Post-Study Drug Period, which will extend beyond the Treatment Period.

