  - **Efficacy**. To evaluate the efficacy of haloperidol and ziprasidone vs. placebo, and to [1] guide titration of study drug dose (see section 7.3.1.[4]), all efficacy outcomes will be assessed during the Treatment Period or longer, depending on the outcome (see section 4.2). While patients are in the ICU and in the Treatment Period, study personnel will determine level of sedation using the RASS and assess for delirium using the CAM-ICU twice daily (except when the participant or their surrogate decision maker refuses the assessment or the participant is unavailable, e.g., in the operating room for an extended period). 41,42,189 When patients are not in the ICU but still in the Treatment Period (i.e., in the hospital and prior to day 14 postrandomization), study personnel will assess them using the RASS and CAM-ICU once daily. In cases where the Post-Study Drug Period extends beyond the Treatment Period, the RASS and CAM-ICU will be completed once daily from the time the Treatment Period ends until the Post-Study Drug Period ends. Time-to-event outcomes (e.g., ICU length of stay, survival, etc.) will be assessed from the time of randomization (entry into the Interventional Trial Phase) until the outcome in question or a censoring event occurs.
  - [2] **Safety**. Patients will be monitored as part of routine ICU care for adverse reactions, including but not limited to NMS, acute dystonia (i.e., muscle spasms and contractions), pseudoparkinsonism, atrial and ventricular dysrhythmias, hyperglycemia, etc. Additionally, study personnel will specifically assess patients for the following safety outcomes.

MIND-USA Protocol Version: 1.15 Confidential Protocol Date: June 22, 2016 22 of 51

- (a) Extrapyramidal symptoms (EPS) according to a modified Simpson-Angus Scale 164 consisting of 5 items: elbow rigidity, wrist rigidity, glabella tap, tremor, and salivation
- (b) Akathisia according to a 10 cm visual analog scale used on days that patients are not comatose or delirious
- (c) QTc prolongation  $\geq$  550 ms as described in section 7.3.1.[5].(a)
- (d) Hyperactive (i.e., agitated) delirium according to RASS and Rescue Protocol use (see section 7.3.3)

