#### 7.6 Schedule of Events

		Pre- Randomization Phase	Interventional Trial Phase			
Variable* (abbreviations on next page)	Enrollment		Treatment Period	Post-Study Drug Period †	Hospital Discharge	3 & 12 Month
Demographics, Comorbidities,  Neuroimaging (CT/MRI) if		Thase	Terrou	Drug Teriou	Discharge	Nonth
available	X					
AUDIT,  ADL,  IADL/FAQ,  IQCODE,  APACHE	***					
II, 241 tobacco and illicit drug use history, employment	X					
SOFA 	X	Daily	Daily	Daily		
Pregnancy test (Beta hCG)	X					
Blood draw: APOE genotyping	X					
Urine collection: cotinine and NNAL	X					
Blood draw: CPD, IL-6, CRP, D-Dimer, sTNFr1, protein-C			Days 0,			
•			1, & 2			
Study drug levels: haloperidol & ziprasidone			Days 0,			
			1, & 2			
Hematology and Chemistry	X	Daily	Daily	Daily		
Co-administered psychoactive meds			D 1	D 1		
sedative/analgesic/antipsychotic		Daily	Daily	Daily		
RASS (target/actual),  CAM-ICU  & CPOT 		2x daily	2x daily	Daily		
BFCRS & DMSS at select participating sites		2x daily	2x daily	Daily		
Hospital-acquired infections (in blood, urine, sputum)		Daily	Daily	Daily		
ABCDE protocol compliance ‡		Daily	Daily			
12-lead ECG (baseline and subsequent ECGs)		X	See section 7.3.1.[5].(a)			
Safety assessments: Modified Simpson-Angus EPS scale, 164			7.3.1.[3].(a)			
visual analog akathisia scale, neuroleptic malignant syndrome,			Daily	Daily		
& dysrhythmia/QTc review			2 willy	2 uii		
Delirium Experience Questionnaire (DEQ) 					X	
Montreal Cognitive Assessment (MoCA) 227,228					X	
Caregiver burden interview & checklist 						X
Long-term telephone follow-up: CAM 169 neuro-						
psychological battery,  ADL,  IADL/FAQ,  EuroQOL						X
quality of life (EQ-5D), 170-172 PTSD/PCL 173, employment						
Health care costs and health status (via Medicare files)						X
Caregiver burden interview & checklist  Long-term telephone follow-up: CAM,  neuro-psychological battery,  ADL,  IADL/FAQ,  EuroQOL quality of life (EQ-5D),  PTSD/PCL  , employment	DACHE II	Acuta Physicle	gia Chronia	Health Evalve		

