# 9.0 Reporting of Adverse Events or Unanticipated Problems involving Risk to Participants or Others

A system has been established to report and track clinical outcomes and adverse events (AEs). Study personnel will monitor the safety of subjects and follow them until the event resolves or is explained.

**9.1** Clinical Outcomes (not considered Adverse Events). In this study of critically ill patients who are at high risk for death or other adverse outcomes due to their underlying critical illness, clinical outcomes, including death and organ dysfunction, will be systematically tracked (collected in the CRF) and will be included as part of the safety and efficacy analyses for this study. For the purposes of reporting, death and organ dysfunction will not be recorded as adverse

MIND-USA Protocol Version: 1.15 Confidential Protocol Date: June 22, 2016 29 of 51

events unless the investigator believes the event may have been caused by study drug and is more severe or prolonged than expected given the underlying critical illness (investigator's discretion). This approach—considering death and organ dysfunction as outcomes rather than adverse events and systemically tracking expected safety outcomes for analysis rather than solely recording individual adverse events—is common in ICU trials because these outcomes/events occur commonly in the ICU and this system mandates that data regarding death, organ dysfunction, and expected safety outcomes be tracked systematically for all patients and analyzed appropriately. All clinical outcomes will be systemically tracked throughout the Treatment Period and the Post-Study Drug Period as described in section 7.3.2. Listed below are events that will be tracked as clinical outcomes and will not therefore be required to be reported as adverse events during this study (unless believed to be study-drug related and more severe or prolonged than expected given the underlying critical illness):

- [1] Death. All deaths occurring within the Interventional Trial Phase will be reported on the CRF in the death summary section. For deaths thought to be caused by study drug, a SUSAR (see section 9.2) will be reported along with the death summary.
- [2] Respiratory failure, including need for mechanical ventilation (invasive or noninvasive) or episodes of hypoxemia
- [3] Circulatory failure, including shock (whether requiring vasopressors or not) and cardiac arrhythmias, and hypertension

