- [4] Hepatic failure or injury leading to increased bilirubin
- [5] Renal failure or injury leading to an increased creatinine or acute hemodialysis
- [6] Coagulation derangements leading to thrombocytopenia
- [7] Stroke and neuropsychological dysfunction that is believed to be newly acquired
- [8] Alterations in vital signs (e.g., temperature, respiratory rate, oxygen saturation)
- [9] Thromboembolisms
- [10] ICU readmissions
- [11] Infections
- [12] Self-removal of devices and invasive tubing and/or monitoring equipment
- [13] The following known adverse reactions to antipsychotics:
  - (a) NMS
  - (b) acute dystonia (i.e., muscle spasms and contractions)
  - (c) pseudoparkinsonism
  - (d) atrial and ventricular dysrhythmias
  - (e) hyperglycemia
  - (f) extrapyramidal symptoms (EPS)
  - (g) tardive dyskinesia
  - (h) akathisia
  - (i) QTc prolongation  $\geq$  550 ms
- 9.2 Adverse Events (AEs), Serious Adverse Events (SAEs), and Serious Unexpected Suspected Adverse Reactions (SUSARs). An Adverse Event (AE) will be any untoward medical occurrence for a patient enrolled in the trial that is not tracked as a clinical outcome (see section 9.1), regardless of whether the event is considered study drug-related or not. If a subject experiences an AE after informed consent is signed but before receiving study drug, the event will be reported as an AE not study drug related. Prior to enrollment, study site personnel will note the occurrence and nature of each subject's medical condition(s). During the study, site

MIND-USA Protocol Version: 1.15 Confidential Protocol Date: June 22, 2016 30 of 51

personnel will note changes in these condition(s) and/or the occurrence and nature of any AEs. All AEs occurring during the Treatment Period and/or the Post-Study Drug Period will be recorded on the CRF. This period is the window of time during which study drug-related adverse reactions are expected based on the duration of the study drug administration plus 4 additional days of Post-Study Drug Period (approximately 4-5 elimination half-lives of haloperidol, the longer acting of the two active study drugs). An AE that later meets criteria for an SUSAR between the start of study drug and hospital discharge will be reported as an SUSAR. If study drug is discontinued as a result of an AE, study personnel will document the circumstances leading to discontinuation of study drug.

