- Time frame: 90 days after first ICU discharge

SO7. Hospital readmission

- Description: Readmission to the hospital after index hospital discharge determined by self-report during follow-up interviews.
- o Time frame: 365 days

SO8. Neuropsychological dysfunction

- Description: Assessed using Telephone Interview for Cognitive Status (TICS),
 Digit Span and Similarities from the WAIS-III, Confusion Assessment Method
 (CAM) Telephone version, Paragraph Recall (both immediate and delayed portions) from the WMS-III, Controlled Oral Word Association Test (COWA), and the Hayling Test. These assessments will be scored in standard fashion and will allow us to characterize cognitive impairment across patients.
- Time frame: 3 and 12 months post-randomization

SO9. Quality of life

- Description: Assessed using the Katz ADL, Employment Questionnaire,
 Functional Activities Questionnaire (FAQ), EQ-5D-3L and a Healthcare Utilization
 Survey.
- Time frame: 3 and 12 months post-randomization

SO10. Post-traumatic stress disorder

- Description: Assessed using the PTSD Checklist (PCL-S, event specific version) with respondents instructed to answer questions in reference to the ICU experience.
- Time frame: 3 and 12 months post-randomization

SO11. Torsades de pointes

- Description: Incidence of tachyarrhythmias determined to be torsades de pointes after review by the site primary investigator, DSMB, and coordinating center.
- Time frame: 14 days plus 4-day post-study drug period (if longer than 14 days)

SO12. Extrapyramidal symptoms

- Description: Occurrence and severity of extrapyramidal symptoms as measured by a modified Simpson-Angus Scale, Akathisia Visual Analogue Scale, and a standardized definition of dystonia
- Time frame: 14 days plus 4-day post-study drug period (if longer than 14 days)

SO13. Neuroleptic malignant syndrome

- Description: Incidence of neuroleptic malignant syndrome identified by the clinical team and confirmed by the site primary investigator and coordinating center
- Time frame: 14 days plus 4-day post-study drug period (if longer than 14 days)

7. Analysis Methods

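### The protocol promises to analyse QTc ≥ 550 ms as a safety outcome and exempts it from routine adverse-event reporting, but the SAP names no QTc outcome; it would appear only as a reason for holding drug

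*SAP*

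**What the plan says.** **Protocol.** Section 9.1 states that clinical outcomes are tracked in the case report form and "will be included as part of the safety and efficacy analyses for this study". Events on its list will not "therefore be required to be reported as adverse events during this study", unless the investigator attributes the event to study drug and judges it worse or longer than the illness would explain. The stated rationale is that this system requires "expected safety outcomes be tracked systematically for all patients and analyzed appropriately". Item [13] of the list, headed "The following known adverse reactions to antipsychotics", has QTc ≥ 550 ms as sub-item (i). Section 9.2 then defines an adverse event so as to leave out anything tracked under 9.1.

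Section 7.3.2[2] says "study personnel will specifically assess patients for the following safety outcomes" and lists four: extrapyramidal symptoms, akathisia, QTc ≥ 550 ms and hyperactive delirium. The QTc item refers back to the hold rule in 7.3.1[5](a). Under that rule QTc is checked before each dose, a value of 550 ms or more is confirmed by 12-lead ECG, and a confirmed value means the dose is held. The Schedule of Events (7.6) also has a daily "dysrhythmia/QTc review" in the Treatment Period and in the Post-Study Drug Period, "which includes the four full calendar days after study drug is discontinued" (7.3.2).

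**SAP.** The drug-safety outcomes in section 6 are SO11 (torsades), SO12 (extrapyramidal symptoms, including akathisia and dystonia) and SO13 (neuroleptic malignant syndrome). SO11 is described as "Incidence of tachyarrhythmias determined to be torsades de pointes after review by the site primary investigator, DSMB, and coordinating center". The exploratory list in section 7 adds a description of torsades incidents and the severity of shock. Section 4, under Presentation of adherence to intervention, describes holds and their reasons within each treatment group, both per patient and per dose opportunity.

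**The concern.** The exemption from adverse-event reporting is a bargain: the event need not be reported one case at a time because it will be analysed systematically. The SAP keeps the exemption in force without supplying the analysis. Followed as written, it gives QTc ≥ 550 ms neither routine adverse-event reporting nor a safety result of its own.

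This matters because protocol 4.1 puts the safety of both drugs against placebo in the primary objective, and protocol 2.5 is devoted to their QT effects. Of the four outcomes in 7.3.2[2], QTc is the only one the SAP does not name. Extrapyramidal symptoms and akathisia are in SO12, and duration of hyperactive delirium is an exploratory outcome.

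**Working it through.** The plan gives no figure to reproduce. The check is mainly a comparison of texts, with three small calculations to bound the size.

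**Step 1. Follow QTc ≥ 550 ms through the two documents.**

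| Question | Where | Answer |
|---|---|---|
| Is it a safety outcome in the protocol? | 7.3.2[2](c); 9.1[13](i) | Yes |
| Is it to be in the safety analyses? | 9.1 | Yes |
| Is it exempt from routine adverse-event reporting? | 9.1, 9.2 | Yes, with the stated exception |
| Is it named among the protocol's Safety Endpoints? | 4.3 | No; arrhythmias including torsades are |
| Is it an SAP outcome, secondary or exploratory? | SAP 6 and 7 | No |
| Can it appear elsewhere in the SAP? | SAP 4, adherence | Yes, as a reason for hold, by arm |

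**Step 2. What the hold tables capture.** A confirmed value of 550 ms or more before a dose leads to a hold, and the SAP tabulates holds with reasons. Confirmed cases found while a dose was due are therefore visible by arm. The patient-level count depends on how long a patient was dosed, but the dose-level table uses dose opportunities as its denominator.

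**Step 3. Days with no dose due.** Monitored days are max(14, d + 4), where d is days on drug (7.3.2, 7.5). This assumes consecutive dosing and no earlier discharge or death.

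- d = 4: 10/14 = 71%
- d = 7, the pilot median (3.3): 7/14 = 50%
- d = 14: 4/18 = 22%

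Protocol 7.5 expects haloperidol to be eliminated within 4 days of the last dose, and ziprasidone sooner. Counting only dosing days plus 4 gives 4/8 = 50% for d = 4 and 4/11 = 36% for d = 7. All of these are shares of days. None is a share of events.

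**Step 4. Can torsades stand in for QTc?** With 0 cases in 187 patients, the exact two-sided 95% upper limit is 1 − 0.025^(1/187) = 1.95%. A torsades count of zero in an arm would still leave a true rate of about 2% possible, and it says nothing about how often QTc reached 550 ms.

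**Step 5. Precision of a by-arm QTc result.** The half-width for a difference at equal rates p is 1.96 × √(2p(1 − p)/187). The rate is not in the documents, so p is assumed.

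- p = 2%: 2.8 points
- p = 5%: 4.4 points
- p = 10%: 6.1 points

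**The case against.** The best reply is that little is lost. The protocol defines outcome (c) by cross-reference to the hold rule, so the reasons-for-hold tables capture nearly all of it as 7.3.2 means it. That stands. Extrapyramidal symptoms are also a hold reason with their own SAP outcome, but they have a separate daily scale, so the parallel is imperfect.

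A reader might infer three stronger things, none of which the documents support.

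- **That QTc data would go unreported.** They would not: the SAP's adherence section describes holds and reasons by arm.
- **That 22% to 71% of events would be missed.** Those are shares of days. No-dose days have falling or no exposure, and the schedule line gives no measurement method for them. The hold rule mentions a sub-item (iii) whose text is not in the copy I read and which might supply one. Nothing shows how many events, if any, fall on those days.
- **That hold counts are biased because an arm with shorter delirium has fewer doses.** This applies only to the patient-level count. The dose-opportunity denominator largely answers it. A count of any QTc ≥ 550 ms has the same weakness, since most readings are taken before doses.

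It is also fair to say that QTc is not alone. Thromboembolism (4.3, 9.1) and hyperglycaemia (9.1) have no SAP outcome either, and the DSMB asked for expedited reporting only of torsades and neuroleptic malignant syndrome (9.3). These points limit the weight of the concern. They do not discharge the commitment in 9.1, because an adherence description is not a safety result with a definition, a time window and patients as the denominator.

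**Conclusion.** The gap is real and modest. The protocol commits to analysing QTc ≥ 550 ms for safety and relieves it of routine adverse-event reporting on that ground; the SAP has no outcome that keeps the commitment. Most of the information would exist in the adherence tables but would not be presented as a safety finding. The possible loss is confined to readings on days without a dose, if such readings exist, and its size is unknown.

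The text comparison rests on no numerical assumption. The precision figures rest on 187 patients per arm and assumed rates of 2% to 10%; at 2% the half-width (2.8 points) exceeds the rate itself, so no between-arm conclusion should be expected. This is a cheap improvement to the SAP. It is not a threat to the trial's conclusions.

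**What to change.** Add one descriptive safety outcome to the SAP: the number and percent of patients per arm with any post-randomisation QTc ≥ 550 ms, 12-lead confirmed where available, over the window already used for SO11–SO13. Report with it the number of QTc readings per patient and the method (12-lead, telemetry strip or software), so that unequal ascertainment can be seen. Include readings from no-dose days only if they are in the database, and show them separately.

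No test, alpha or change to the 550 ms entry and hold rule is needed. The SAP gives its missing-data figures as of before unblinding, so at that stage the outcome could be added without sight of results by arm.

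Optional: highest post-randomisation QTc in bands of < 500, 500–549 and ≥ 550 ms, since 500 ms is the threshold used in protocol 2.5. The protocol does not commit to this. Values below 550 ms will mostly be unconfirmed telemetry or software readings and should not be set against the baseline 12-lead ECG as if comparable.

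The cost is one extra table with mixed measurement methods and low precision. No new data collection is needed if QTc values or a ≥ 550 ms flag are in the database; the protocol requires pre-dose values to be documented, but the documents do not say whether they were entered.

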2.2 Objectives

The MIND-USA study is a multicenter, double-blind, randomized, placebo-controlled trial investigating the effects of intravenously (IV) administered typical and atypical antipsychotics (haloperidol and ziprasidone) on delirium in critically ill patients. The study evaluates the following aims:

- Aim 1: To determine whether haloperidol or ziprasidone administered to delirious medical/surgical ICU patients will increase days alive without delirium and coma (measured as delirium/coma-free days [DCFDs]) over a 14-day study period compared with placebo.
- **Aim 2:** To determine whether haloperidol or ziprasidone will improve 30-day, 90-day, and 1-year survival compared with placebo.
- **Aim 3:** To determine whether haloperidol or ziprasidone will reduce ICU length of stay (LOS) (i.e., time to ICU discharge) compared with placebo.
- Aim 4: To determine whether haloperidol or ziprasidone will improve long-term neuropsychological outcomes, functional independence, quality of life, and post-traumatic stress disorder symptoms at 3-month and 1-year follow-up compared with placebo.

3. Study Methods

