"Time 0" will be the time of randomization for each of these outcomes, with the exception of ICU readmission; for this outcome, "time 0" will be the time of the first ICU discharge, and only patients who survived their first ICU admission will be included.

Long-Term Outcomes

We will use multivariable regression to analyze the relationship between treatment group and scores measuring long-term neuropsychological, quality of life, and PTSD outcomes as outlined in the Outcomes section above. Depending on the distribution of each outcome, we will use linear regression, negative binomial regression, or proportional odds logistic regression, as appropriate. These models will not include covariates other than treatment.

For each outcome, we will have separate models for 3- and 12-month scores. At each time point, we include all patients with available outcome data, using inverse probability weighting to account for patient death and attrition. To decrease reliance on a few highly influential observations, we will truncate weights at the top 1 percentile.

As a sensitivity analysis, we will also define long-term outcomes using the unadjusted composite endpoint approach (reference: Lachin) to deal with outcomes truncated due to death or loss to follow up. The composite endpoint will be defined as:

- If the patient dies prior to assessment: days between randomization and death
- If the patient survives and is successfully assessed: days between randomization and planned assessment (constant) + assessment score

For example, if we are analyzing a 3-month outcome, the constant would be 90. Differences between the composite end point distribution amongst groups will be assessed using the Kruskal-Wallis test.

Adjusted Analyses

We will adjust all coefficient variances using Huber-White sandwich estimation, clustered by study site. This will help account for unmeasured variability and correlation among patients within a given site.

In-Hospital Continuous Outcomes

We will use proportional odds logistic regression for continuous outcomes (delirium/coma-free days; delirium duration [any, hyperactive, and hypoactive]; coma duration; mean CV SOFA and lowest mean arterial pressure); this method assumes an ordinal outcome but does not assume that it follows a specific statistical distribution.

If the overall test for treatment vs our primary outcome (DCFDs) is significant at the 5% level, we will report individual treatment tests vs placebo at the 2.5% level.

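### The SAP's long-term sensitivity composite adds raw scores without stating any instrument's direction, so on a higher-is-worse instrument the sickest assessed survivors would rank best.

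*SAP*

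**What the plan says.** SAP Section 7, Unadjusted Analyses, Long-Term Outcomes, covers "scores measuring long-term neuropsychological, quality of life, and PTSD outcomes". Its main analysis is regression with inverse probability weights. A composite endpoint is added as a sensitivity analysis "to deal with outcomes truncated due to death or loss to follow up". It has two parts:

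- Deaths: "If the patient dies prior to assessment: days between randomization and death".
- Assessed survivors: "If the patient survives and is successfully assessed: days between randomization and planned assessment (constant) + assessment score". The SAP's example constant is 90 for a 3-month outcome.

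The test is an omnibus one: "Differences between the composite end point distribution amongst groups will be assessed using the Kruskal-Wallis test".

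SAP Section 6 lists the instruments. The only remark on scoring stands under SO8, the cognitive tests: "These assessments will be scored in standard fashion". For PTSD, SO10 says only "Assessed using the PTSD Checklist (PCL-S, event specific version", then how respondents are instructed. SO9 lists instruments and nothing more, and so do the protocol's endpoint list (Section 4.2), Section 7.4 and the schedule of events. SAP Section 2.2, Aim 4, asks whether treatment "will improve long-term neuropsychological outcomes, functional independence, quality of life, and post-traumatic stress disorder symptoms".

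**The concern.** A patient who lives longer before dying gets a higher value, and an assessed survivor gets at least the constant. The composite therefore makes sense only if higher means better throughout. Aim 4 mixes outcomes where improvement means more (functional independence, quality of life) with one where it means less (PTSD symptoms). One additive rule on raw scores cannot be assumed to fit all of them.

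Ranking does not repair this. Kruskal-Wallis gives the same result if the whole order is reversed, but here only the survivors' part would run backwards while deaths stay at the bottom. On a higher-is-worse instrument, a drug that both saves lives and reduces symptoms would have one effect set against the other. The sensitivity analysis could then seem to contradict the weighted regression it is meant to check.

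**Working it through.** The plan states no figure for this composite, so there is none to reproduce. The check has four steps.

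**1. Ranks in a small example.** Constant 90 from the SAP; a 0-30 scale with higher worse is assumed.

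| Patient | As written | Rank | Reversed, 90 + (30 - score) | Rank |
|---|---|---|---|---|
| Died day 10 | 10 | 1 | 10 | 1 |
| Died day 60 | 60 | 2 | 60 | 2 |
| Survivor, score 0 (best) | 90 | 3 | 120 | 5 |
| Survivor, score 15 | 105 | 4 | 105 | 4 |
| Survivor, score 30 (worst) | 120 | 5 | 90 | 3 |

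**2. Break-even, with no scale range or SD assumed.** Inputs: 40% control mortality and a 14-point difference (Protocol 11.2); follow-up of survivors f = 0.80 (Protocol 11.3) or 0.91 (Protocol, missing-data paragraph); 40% vs 35% is an assumed smaller difference. Let w be the chance that a drug survivor has fewer symptoms than a placebo survivor (0.50 = no benefit). The formula assumes the same distribution of death times in both arms and a higher-is-worse score.

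Death share among analysed patients, with mortality p: d = p / (p + (1 - p)f), and s = 1 - d. The subscripts t and c mean drug and placebo.

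Chance that a drug patient outranks a placebo patient, as written: s_t d_c + 0.5 d_t d_c + s_t s_c (1 - w). With the score oriented, w replaces (1 - w).

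At 40% vs 26% and f = 0.80:

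- d_c = 0.40/0.88 = 0.4545; d_t = 0.26/0.852 = 0.3052
- s_t d_c = 0.3158; 0.5 d_t d_c = 0.0694; s_t s_c = 0.3790
- survival alone (w = 0.5): 0.3158 + 0.0694 + 0.1895 = 0.575
- setting the as-written value to 0.5: 1 - w = (0.5 - 0.3852)/0.3790 = 0.303, so w = 0.697

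| Mortality | w that cancels, f = 0.80 | f = 0.91 |
|---|---|---|
| 40% vs 26% | 0.697 | 0.673 |
| 40% vs 35% (assumed) | 0.580 | 0.570 |
| equal | 0.500 | 0.500 |

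**3. Illustrative rejection rates.** All score inputs are assumed: mean 34, SD 12-16, limits 17-85, front-loaded death times, both drugs equally effective. There are 187 patients per arm, 80-91% of survivors are assessed, and the test is a three-group Kruskal-Wallis at 5% (3,000 runs per scenario). A 4-point benefit corresponds to w of about 0.57-0.59.

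| Mortality | Symptom benefit | Oriented | As written |
|---|---|---|---|
| 40% vs 26% | none | 66-68% | 66-68% |
| 40% vs 26% | 4 points | 92-97% | 19-33% |
| 40% vs 35% | none | 12% | 12% |
| 40% vs 35% | 4 points | 33-52% | 5-6% |
| 40% vs 40% | 4 points | 10-17% | 10-17% |

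In the last row the drug-minus-placebo difference in mean rank changes from between +10 and +16 (oriented) to between -10 and -16 (as written). A separate simulation on other assumed values (score 0-50, SD 10, uniform death times, 80% assessed) gave the same pattern: 26% as written vs 95% oriented at 40% vs 26% with a 3-point benefit. With no effect at all it rejected about 5% of the time either way.

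**4. Living patients with no value (a separate wording point).** Protocol 11.3 expects 561 x 0.69 = 387 survivors at 12 months, and 387 x 0.80 gives its 310 tested. Unassessed: 387 x 0.09 = 35 at 91% follow-up, or 387 x 0.20 = 77 at 80%. That is 6% to 14% of 561. The formula has no line for them.

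**The case against.** The strongest reply has four parts, each partly right.

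- **The harm depends on coding the documents do not give.** This stands. Neither document says that a higher PCL-S or other instrument score is worse. The omission is certain; the consequence is conditional.
- **An analyst would orient the scores anyway, since Aim 4 shows which way improvement runs.** Aim 4 gives the direction of improvement, not how each instrument is coded. The SAP settles details as fine as truncating weights at the top 1 percentile but not this one. Deciding it after unblinding would be an undocumented choice that changes the result.
- **The analysis is minor.** It is one unadjusted sensitivity analysis of secondary outcomes. Because the SAP names only an omnibus test, the reversed order at equal mortality would mislead only if mean ranks or medians were reported. This limits the weight of the point but does not remove it.
- **The cited worst-rank article may deal with orientation.** The SAP gives only the reference, and its title can neither confirm nor rule this out. The argument here rests on the printed formula alone.

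A reader might also infer that no long-term scale in either document has a direction. That goes too far: the protocol's missing-data paragraph defines a four-level cognitive outcome running from normal (1) to death (4). It belongs to a different analysis and does not enter this composite.

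**Conclusion.** The point holds as a conditional one. The SAP prints one additive rule for all long-term scores, and it mis-ranks survivors on any instrument coded higher-is-worse.

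A reader might infer that a modest symptom benefit wipes out the survival signal at the protocol's 14-point mortality difference. It does not. The 4-point case there is a large loss of power. Full cancellation needs w of 0.67-0.70, which for normal scores is about 0.63-0.73 SD, or roughly 8-12 points on the assumed scale. Only at the assumed 40% vs 35% does a modest benefit (w about 0.57-0.58) cancel the survival signal.

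Nor does the flaw create false positives: type I error stays near 5%, and with no difference in survivors' scores orientation makes no difference. The primary outcome, the inverse-probability-weighted regressions and any higher-is-better instrument are unaffected. The break-even values rest on the mortality and follow-up figures and on equal death-time distributions; the rejection rates also rest on assumed score distributions.

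**What to change.** Before unblinding, add to the SAP's long-term outcomes text the direction of each instrument. Where higher is better, keep constant + score. Where higher is worse, use constant + (maximum possible score - score). For a score with no fixed maximum, use any order-reversing recode that keeps all assessed survivors above all deaths.

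Separately from orientation, stop describing the composite as handling loss to follow-up, because living, unassessed patients receive no value, and report their number by arm.

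The cost is a few sentences and a recode, with no new data and no new model.
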